9.4 Study Drug Accountability

An accurate and current accounting of the dispensing and return of study drug for each subject will be maintained on an ongoing basis by a member of the study site staff. The number of study drug dispensed and returned by the subject will be recorded.

9.5 Measures of Treatment Compliance

Subjects will be asked to keep a patient diary noting the day and date they take their study drug and any adverse events. They will be asked to bring their patient diary to each study visit along with all used and unused study drug containers.

10 HYPERKALEMIA MANAGEMENT

One of the most significant complications of the study medications is hyperkalemia. This risk is of particular importance in this study population as diabetic patients with chronic kidney disease are at increased risk for selective aldosterone deficiency, predisposing them to the development of hyperkalemia. Mild to moderate hyperkalemia is generally not associated with significant cardiac toxicity, especially when it is chronic (e.g., in dialysis patients) or slowly developing. In contrast, severe (> 6.5 mEq/L) or rapidly developing hyperkalemia is likely to be associated with the development of ECG abnormalities ranging from peaking of the T- wave; to atrial, AV nodal and ventricular conduction delays; and ultimately, with very severe hyperkalemia, to ventricular fibrillation.

Dietary intake of potassium is a major factor in producing hyperkalemia and transient dietary increases in potassium intake can precipitate hyperkalemia in our patients. For example, a single high potassium meal prior to blood draw could result in high potassium at the time of the draw but later on a repeat the potassium may be much lower, as much as 1 mEq/L lower.

Decreased cellular uptake of potassium occurs when insulin is relatively deficient. Even a patient who is not on insulin can have relative insulin deficiency (also known as insulin resistance). Generally decreased cellular uptake of potassium occurs when a patient has ingested a high potassium diet but does not have enough insulin to drive potassium into the cell. This can result in transient hyperkalemia.

Factors that impair renal excretion of potassium and can contribute to hyperkalemia in addition to the study medication include: 1) decreased GFR; 2) drugs including NSAIDS (e.g. ibuprofen), COX-2 inhibitors (e.g. celecoxib) and 3) any process which decreases distal tubular flow rate such as can occur in the setting of volume depletion.

One or all of the above factors can be operative in the same patient. For example, a volume depleted patient can have relative insulin deficiency, a high potassium intake and have taken NSAIDS for pain while ingesting the study medication.

Subjects will be counseled to avoid medications that may increase the risk of hyperkalemia, such as non-prescription non-steroidal anti- inflammatory medications, and potassium-containing salt substitutes. All subjects will be monitored for the development of hyperkalemia at each follow-up visit and an ECG will be obtained for any potassium value > 6.0 mEq/L.

The aggressiveness of treatment of hyperkalemia will depend on the degree of elevation and the presence or absence of ECG findings.

10.1 Treatment of hyperkalemia for Potassium > 5.0 meq/L: Dietary potassium

If during follow-up, a subject's potassium level increases to > 5.0 mEq/L, he/she will be prescribed a low potassium diet (0.7-0.8 meq/kg/day to a maximum daily intake of 60

meq/day). An initial step would be to restrict potassium in the diet. Input from a dietician can be helpful.

There is potassium in most foods, but certain foods are especially high in potassium and should be avoided. Some high potassium foods can be eaten after leaching the potassium by soaking. Many salt substitutes are potassium chloride and should be avoided. Fruits and vegetables should be limited to four servings per day. Dairy products should be limited to 1 cup/day.

High Potassium Foods (avoid):

Fruits and juice: apricots, avocado, banana, cantaloupe, honeydew, dried fruit (dates, raisins, prunes, figs), citrus fruits (orange, grapefruit, nectarines)

Vegetables: artichoke, butter beans, dried peas or beans, potatoes (unless leached), sweet potatoes, Swiss chard, winter squash.

Other: chocolate, molasses, nuts, peanuts

Medium potassium foods: Limit to one serving (1/2 cup)/day:

Fruits: blackberries, cherries, peach (1), pear (1), raspberries, strawberries, watermelon (1 cup), plums (2)

Vegetables: broccoli (cooked), carrot, mushroom, peas, corn, cabbage, eggplant, spinach (cooked), pumpkin, tomato, potato (leached), beets

Low potassium foods (note that portion size is 1/2 cup, eating a large amount of a lower potassium food will make it a higher potassium food)

Fruits (including juice): Apple, blueberries, cranberries, grapes, tangerine (1 small)

Vegetables: green beans, wax beans, cucumber, green pepper, lettuce, yellow squash

Leaching vegetables: For potatoes, sweet potatoes, carrots, beets and rutabagas:

Peel and slice vegetables 1/8 inch thick

Rinse

Soak for a minimum of two hours in warm water, using 10 times the amount of water to the amount of vegetables. If soaking longer, change the water every few hours

Rinse under warm water

Cook with five times the amount of water to the amount of vegetable

10.2 Treatment of hyperkalemia for Potassium > 5.5 meq/L

In addition to a low potassium diet, if the potassium level increases to >5.5 mEq/L, conservative measures should be instituted.

Possible approaches include:

Increase in diuretics if volume depletion is not a concern. Volume depletion could worsen hyperkalemia

Administration of chronic alkali supplements, such as sodium bicarbonate 1300mg bid if acidosis is present

Liberalization of salt intake (if volume status and uncontrolled blood pressure are not concerns)

Chronic use of low-dose sodium polystyrene sulfonate (15-30 grams 3x/week)

10.3 Treatment of hyperkalemia for Potassium > 6.0 meq/L

If the potassium level is > 6.0 mEq/L, the study medication will be held until the level decreases to < 5.5 mEq/L.

Acutely to treat the potassium:

An ECG should be checked. If there are no ECG changes and potassium level is < 6.5, then Kayexalate alone (60 grams) may be sufficient. If there are ECG changes, treatment would include insulin/glucose, beta-agonists and possibly calcium and bicarbonate. If there are ECG changes or if the potassium level is > 6.5 meq/L, the patient should be treated in the emergency room. If there are ECG changes, the patient should be placed on a cardiac monitor.

Reinstitution of Study Medication

If the potassium level was > 6.5, then the study medication will be permanently discontinued and the patient will be removed from the trial. If this is the second episode where potassium > 6.0, then the study medication will be permanently discontinued and the patient will be removed from the trial.

Recheck potassium level 7- 14 days after discontinuation. If K+ is > 5.5 mEq/L, do not restart study medications. Repeat potassium again in 7-14 days. If K+ is \leq 5.5 mEq/L, the study medication will be reinstated at 50% of prior dose.

If the study medication was restarted, check potassium level again in two weeks, if K+ is:

- o > 6.0: stop study the study medication permanently
- o 5.5-6.0: treat K+, maintain current dose of the study medication
- o < 5.5: mEq/L and patient is on at least 12.5 mg spironolactone, increase spironolactone to 25mg daily.

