3.1.1.1 Common Side Effects

- Hyperkalemia: We anticipate that approximately 1% of patients may develop serious hyperkalemia that may warrant discontinuation. However this may be considerably higher in patients with GFR of 40-50 ml/minute who will constitute a minority of the patients in the trial.
- Increases in BUN and creatinine

- Hypomagnesemia
- Gynecomastia or breast discomfort. Gynecomastia is a well-described adverse effect of spironolactone and is related to dose and duration of treatment; we anticipate that approximately 10% of patients may develop gynecomastia that may warrant discontinuation. Generally, discontinuation of treatment results in resolution of gynecomastia.

3.1.1.2 *Other Side Effects*

- Cardiovascular: Vasculitis
- Central nervous system: Ataxia, confusion, drowsiness, headache, lethargy
- Dermatologic: Erythematous maculopapular rash, Stevens-Johnson syndrome, toxic epidermal necrolysis, urticaria
- Endocrine & metabolic: Amenorrhea
- Gastrointestinal: Abdominal cramps, diarrhea, gastritis, gastrointestinal hemorrhage, gastrointestinal ulcer, nausea, constipation, flatulence, vomiting
- Genitourinary: Impotence, irregular menses, postmenopausal bleeding
- Hematologic & oncologic: Agranulocytosis, malignant neoplasm of breast
- Hepatic: Hepatotoxicity
- Hypersensitivity: Anaphylaxis
- Immunologic: DRESS syndrome
- Renal: Increased BUN, renal failure, renal insufficiency
- Miscellaneous: Fever

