4. STUDY OBJECTIVES

4.1 Primary Objective

Specific Aim 1: To conduct a prospective open label proof-of-concept clinical trial in 50 patients with Type II diabetes evaluating the effects of MRA + Patiromer on LV mass and plaque regression over 12 months of treatment by MRI. Primary outcome measures will be change in LV mass of patients receiving Patiromer + Spironolactone at the end of 12 months and end-point of safety during this period. An additional co-primary measure will include percent change in atheroma volume (PAV) in the thoracic aorta on Patiromer + Spironolactone at the end of 12 months. Additional secondary measures will include central aortic blood pressure, 24-hour mean systolic blood pressure and measures of insulin resistance (HOMA-IR) at 12 weeks.

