5. STUDY DESIGN

OVERALL STUDY DESIGN AND EXECUTION

This will be a multicenter trial that will provide a logical extension to a recently funded NIH sponsored trial to assess efficacy of Spironolactone in patients with Type 2 DM and CKD (GFR 20-90ml/m²) compared to placebo (NCT02169089). In this extension study to

NCT02169089, patients with GFR 20-70 ml/m² who are hyperkalemic at baseline (with or without RAAS therapy) precluding an MRA and/or develop hyperkalemia on an MRA (**FIGURE 3**) will be enrolled and placed on Spironolactone. The primary efficacy variables being LV mass change and in patients treated with Patiromer and MRA. Our hypothesis is that Patiromer use in conjunction with an MRA will result in more effective blood pressure lowering, LV mass regression and plaque regression due to more effective lowering of aldosterone and inflammation. The primary safety variable is development of serious hyperkalemia on treatment in Patiromer+Spironolactone arm. Several secondary variables will be obtained, including monocyte-macrophage inflammatory indices, central aortic blood pressure and 24-hour blood pressure at 6 weeks and arterial compliance.

Figure 3.

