6. CRITERIA FOR EVALUATION

6.1 Aim 1A Protocol

[figure not shown]
Cardiac and aortic MRI images will be obtained at Visit 2 and Visit 8. Patients will be imaged on a 3T 32-channel whole-body MR imaging system (Trio 3.0T, Siemens, Erlangen) with maximum gradient amplitude of 60 mT/m and a slew rate of 400 mT/m/ms. The system's integrated body coil will be used for radiofrequency signal transmission. Signal reception will be accomplished with the use of two flexible 6-element phase array body coil matrix in combination with the spine coil. After acquiring the low resolution, images for localization, each patient will undergo trueFISP cine imaging (8–10 short axis and 3 LV long axis with 20–30 cardiac phases depending on heart rate). Additional details on sequence parameters are provided on the Manual of operations. Following acquisition of cardiac MRI images, fat suppressed 3D turbo-spin echo (TSE) images using, dark blood acquisition protocol, based on SPACE sequence with 1mm³ resolution. MRI parameters are as follows: TR/TE= R-R interval/22ms, field of view FOV=320x272 mm², slices per slab 56, averages =1.7, bandwidth-BW=781Hz/px, echo spacing=2.9ms, turbo factor= 45, echo train/slice=3.

Quantitative evaluation:

LV mass estimation: the images from the participating sites will be loaded onto a dedicated workstation (*Leonardo*TM, Siemens Medical Solutions, Erlangen, Germany). Using specialized software (*Argus*TM, Siemens Medical Solutions, Erlangen, Germany), the short-axis views of the heart will be automatically sorted into slice positions (rows)

and cardiac phases (columns). End-diastole (ED) and end-systole (ES) will be visually identified as those phases with maximum and minimum area in a midventricular short-axis view of the LV cavity, using the position of the mitral and aortic valve as an aid to identify the phase of the cardiac cycle. The images will be cropped and zoomed to enhance detection of the myocardium-blood pool and myocardium-fat interfaces.

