9 STUDY TREATMENTS

9.1 Method of Assigning Subjects to Treatment Groups

Up to 50 eligible patients will participate in the study. All study participants will undergo a two week run-in period with Patiromer. Then study medication will be commenced at 12.5 mg Spironolactone and Patiromer 8.4 g/d and escalate to 25 mg Spironolactone over

4 weeks. If needed, to manage K⁺, Patiromer will increase to 16.8 g/d. Then the treatment phase will commence with tolerated dose of Spironolactone along with Patiromer for 48 weeks.

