13 DISCONTINUATION OF SUBJECTS

13.1 Early Discontinuation of Study Drug

A subject may be discontinued from study treatment at any time if the subject, the investigator, or the Sponsor feels that it is not in the subject's best interest to continue. The following is a list of possible reasons for study treatment discontinuation:

Subject withdrawal of consent (or assent)

Subject is not compliant with study procedures

Adverse event that in the opinion of the investigator would be in the best interest of the subject to discontinue study treatment

Protocol violation requiring discontinuation of study treatment

Lost to follow-up

Sponsor request for early termination of study

Positive pregnancy test (females)

If a subject is withdrawn from treatment due to an adverse event, the subject will be followed and treated by the Investigator until the abnormal parameter or symptom has resolved or stabilized.

All subjects who discontinue study treatment should come in for an early discontinuation visit as soon as possible and then should be encouraged to complete all remaining scheduled visits and procedures.

All subjects are free to withdraw from participation at any time, for any reason, specified or unspecified, and without prejudice.

Reasonable attempts will be made by the investigator to provide a reason for subject withdrawals. The reason for the subject's withdrawal from the study will be specified in the subject's source documents.

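### Section 10.3 takes patients with severe or repeated hyperkalemia out of the trial, against Section 13.1, and does not name the drug to be held

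*Combined protocol and SAP*

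**What the plan says.** Section 10.3 of the protocol sets two triggers for permanent removal. The first is "If the potassium level was > 6.5, then the study medication will be permanently discontinued and the patient will be removed from the trial". The second begins "If this is the second episode where potassium > 6.0, then the study medication will be permanently discontinued" and ends with the same removal clause.

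Section 13.1 covers all subjects who discontinue study treatment and lists adverse events among the possible reasons. It asks for an early discontinuation visit, after which these subjects "should be encouraged to complete all remaining scheduled visits and procedures". It makes no exception for hyperkalemia.

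The outcomes affected are set elsewhere:

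- Section 4.1: "Primary outcome measures will be change in LV mass of patients receiving Patiromer + Spironolactone at the end of 12 months". Percent change in aortic atheroma volume (PAV) at 12 months is an additional co-primary measure.
- Section 6.1: "Cardiac and aortic MRI images will be obtained at Visit 2 and Visit 8".
- Section 5: "The primary safety variable is development of serious hyperkalemia on treatment in Patiromer+Spironolactone arm".

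The hold at potassium above 6.0, the permanent stop and the half-dose restart in Section 10.3 all refer only to the study medication. Spironolactone is named once, in the last bullet, where it goes back up to 25 mg. Patiromer is not mentioned in that section.

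**The concern.** There are two separate problems.

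The first is follow-up. A patient removed from the trial has no remaining visits to complete, so Sections 10.3 and 13.1 give opposite instructions for the same person. If 10.3 is followed, the Visit 8 scan is lost in exactly those patients in whom the combination failed to control potassium. The missing efficacy data would then depend on the primary safety event. A mean over the remaining patients would tend to look better than the mean over everyone treated, if those removed early gained less.

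The second is drug safety. Section 9.1 uses the term study medication for spironolactone and patiromer together. Read that way, 10.3 tells a site to hold or halve the potassium binder while potassium is dangerously high. Sections 9.1 and 9.3.3 point the other way and raise patiromer as potassium requires.

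**Working it through.** **Text comparison**

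| Situation | Section 10.3 | Section 13.1 |
|---|---|---|
| K above 6.5 | Drug stopped for good, patient removed | Drug stopped, early discontinuation visit, remaining visits encouraged |
| Second K above 6.0 | Drug stopped for good, patient removed | Same as above |
| K above 6.0 after restart | Drug stopped for good, removal not mentioned | Same as above |

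The third row shows that 10.3 also disagrees with itself. A patient restarted after an episode above 6.0 who exceeds 6.0 again is having a second episode. The general rule removes that patient, while the post-restart bullet only stops the drug.

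**Which drug.** Section 10 treats the study medication as a contributor to hyperkalemia, and the last bullet of 10.3 adjusts spironolactone. Both point to spironolactone. Against that, Section 9.1 applies the term to both drugs, and 10.3 uses the plural once in its restart rule. On either reading, 10.3 does not say what happens to patiromer.

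**Size of the missing-data effect.** The plan gives no figure to reproduce, so this is a check of scale.

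Inputs:

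- Rate q = 0.01, from Section 3.1.1.1: "approximately 1% of patients may develop serious hyperkalemia that may warrant discontinuation". That this rate matches the 10.3 removal triggers is an assumption.
- n = 50, from Section 9.1: "Up to 50 eligible patients will participate in the study". Enrollment closed early and the final number is not given, so n = 25 and n = 10 are assumed alternatives.
- f, the share of benefit kept by removed patients: 0 or 0.5, assumed.
- Mean effect in retained patients: 0.5 SD of the change, assumed.

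Expected removals = n × q. Chance of at least one = 1 − (1 − q)^n.

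| n | Expected removals | Chance of at least one |
|---|---|---|
| 50 | 0.5 | 39.5% |
| 25 | 0.25 | 22.2% |
| 10 | 0.1 | 9.6% |

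Relative overstatement of the all-treated mean = 1/(1 − q(1 − f)) − 1:

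- f = 0: 1/0.99 − 1 = 1.0%
- f = 0.5: 1/0.995 − 1 = 0.5%

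Absolute bias at f = 0 is q × 0.5 SD = 0.005 SD. The standard error of a mean change is 1/√n SD, which is 0.141 SD at n = 50 and 0.200 SD at n = 25. The bias is therefore about 1/28 and 1/40 of the standard error.

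**If the rate is higher.** Section 3.1.1.1 says it may be considerably higher at GFR 40–50 but gives no number. The rates below are assumed, with n = 50 and f = 0.

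| Assumed rate | Expected removals | Chance of at least one | Bias (rate × 0.5 SD) | Bias / 0.141 |
|---|---|---|---|---|
| 5% | 2.5 | 92.3% | 0.025 SD | 0.18 |
| 10% | 5.0 | 99.5% | 0.050 SD | 0.35 |
| 15% | 7.5 | >99.9% | 0.075 SD | 0.53 |

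**The case against.** The strongest reply is that 10.3 is a specific safety rule and 13.1 a general one. Section 13.1 only encourages attendance. It cannot cover literally everyone, because its list of reasons includes withdrawn consent and loss to follow-up. The post-restart bullet suggests that removal is loose wording for stopping the drug. This is a fair account of how the text may have arisen, but it leaves a written instruction to remove patients who could have been scanned.

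No primary safety information is lost: the triggering event has already happened, Section 12.1 counts potassium above 6.0 as an adverse event, and Section 13.1 follows adverse-event withdrawals until the problem resolves or stabilises. That stands. The loss is confined to the efficacy scans.

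Section 4.1 can be read as targeting patients still on treatment at 12 months. On that reading an off-drug scan is outside the target and there is no bias to correct. That also stands; the bias argument applies only if the target is all treated patients. The schedule of events, as extracted, marks an MRI at Visit 6, so some removed patients may have an earlier scan, though not the 12-month one.

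On the drug name, context favours spironolactone, and one packet is the starting patiromer dose, so halving it is awkward. That makes the literal reading unlikely, but a safety rule should not depend on inference.

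Finally, the COVID-19 plan closed enrollment permanently. Three of the four sites had enrolled nobody, and all active participants were in the treatment phase. The wording changes can now help only those still in follow-up.

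**Conclusion.** The concern holds, at minor severity. The contradiction between 10.3 and 13.1 and the unnamed drug are plain on the text and need no assumption.

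The effect on the estimate is small at the protocol's own rate: half a patient expected at the ceiling of 50, and a bias of 0.005 SD against a standard error of 0.141 SD. This rests on the 1% rate matching the removal triggers, a 0.5 SD effect, no benefit in removed patients, and a target of all treated patients. The rate is the weakest input. Section 3.1.1.1 describes patients with GFR 40–50 as a minority, yet Section 7.2 admits GFR below 60 regardless of proteinuria and requires screening potassium of at least 4.6, and Section 7.3 excludes only GFR below 15. Even at an assumed 15%, the bias stays near half a standard error.

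The ambiguity about patiromer is a matter of patient safety and does not depend on these figures.

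**What to change.** 1. In Section 10.3, delete the clause that removes the patient from the trial, in both places, and refer to Section 13.1 for follow-up. Keep every drug-stopping threshold as it is. This also brings the two rules into line with the post-restart bullet.
2. In the SAP announced in Section 15, state that available Visit 8 data from these patients enter the LV mass and PAV analyses. This settles the target as all treated patients.
3. In the hold, stop and half-dose restart rules of Section 10.3, replace the general term with spironolactone, apparently the drug meant, and say whether patiromer continues.

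The cost is a wording amendment, one sentence in the SAP, and a few exit visits and MRIs off drug. The scans become possible, not certain, because attendance is only encouraged. The estimate may come out slightly less favourable. Items 1 and 3 help only patients still in follow-up; item 2 can be adopted at any time before the final analysis.

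### Section 10.3 gives opposite orders at a potassium of exactly 5.5 mEq/L and does not name the drug to be held and halved

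*Combined protocol and SAP*

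**What the plan says.** Section 10.3 applies once potassium exceeds 6.0 mEq/L.

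- **Hold line:** "the study medication will be held until the level decreases to < 5.5 mEq/L".
- **Recheck, 7 to 14 days later:** above 5.5, "do not restart study medications"; at or below "5.5 mEq/L, the study medication will be reinstated at 50% of prior dose".
- **Two weeks after restart:** above 6.0, stop for good; in the middle band, "5.5-6.0: treat K+, maintain current dose of the study medication"; below 5.5 "mEq/L and patient is on at least 12.5 mg spironolactone, increase spironolactone to 25mg daily".
- **No restart at all** after a value above 6.5 or a second value above 6.0.

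Section 9.1 shows what study medication covers: "Then study medication will be commenced at 12.5 mg Spironolactone and Patiromer 8.4 g/d and escalate to 25 mg Spironolactone". It adds that, where needed for potassium, "Patiromer will increase to 16.8 g/d", and that the treatment phase runs at whatever spironolactone dose is tolerated. Section 9.3.3 likewise raises patiromer from one packet (8.4 g) to two (16.8 g) according to potassium, and leaves dose adjustment in general to the study physician.

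**The concern.** This is a safety rule for a patient who has just had a potassium above 6.0 mEq/L. Someone applying it should be able to read three things from it: the value at which treatment resumes, which drug is affected, and the next dose step. Section 10.3 falls short on each, to different degrees.

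The most consequential point is the drug. If staff take study medication to mean what Section 9.1 says it means, the patient loses the potassium-lowering agent at the moment it is most needed, and later gets it back at half dose. The threshold conflict is narrower, but it is a plain contradiction. While the wording stands, adherence to Section 10.3 cannot be checked at these points, because more than one action can be defended from the text.

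**Working it through.** The plan states no figure to reproduce. The check applies the rules as written.

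**1. Threshold.** The hold ends when K < 5.5; the recheck line restarts when K ≤ 5.5.

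| K (mEq/L) | Hold line | Recheck line | Agree? |
|---|---|---|---|
| 5.4 | release | restart | yes |
| 5.5 | keep holding | restart | **no** |
| 5.6 | keep holding | do not restart | yes |
| 6.0 | keep holding | do not restart | yes |

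The conflict is confined to one value. The cut-points in Section 10.3 are given to one decimal; if the laboratory reports the same way (an assumption), 5.5 is an ordinary result.

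**2. Which side of 5.5 does the rest of the protocol favor?** It is mixed. The two-week list bars a dose increase at 5.5 but keeps the patient on treatment. Section 9.3.3 starts spironolactone at once for a screening potassium of 5.3 to 5.5 and delays it only above 5.5. Section 10.2 begins conservative measures only above 5.5. So the documents do not settle which of the two lines is right.

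**3. Drug.** In Section 10.3 the hold, restart and 50% lines name no drug. Spironolactone is named only in the last two-week branch. Patiromer is not mentioned anywhere in Section 10; the only binder named there is polystyrene sulfonate (Kayexalate). Taking the Section 9.1 meaning and applying 50%:

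- spironolactone: 0.5 × 25 = 12.5 mg; 0.5 × 12.5 = 6.25 mg
- patiromer: 0.5 × 16.8 = 8.4 g/d; 0.5 × 8.4 = 4.2 g/d, which is half a packet

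The patiromer line runs against Sections 9.1 and 9.3.3, where rising potassium is a reason to give more.

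**4. Step after a 6.25 mg restart.** A prior dose of 12.5 mg is possible: it is a starting dose under Sections 9.1 and 9.3.3, and patients may stay on a tolerated dose below 25 mg. Halved, it gives 6.25 / 25 = 25% of the target dose, a level the protocol does not name. At the two-week check:

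| K (mEq/L) | Restarted at 12.5 mg | Restarted at 6.25 mg |
|---|---|---|
| above 6.0 | stop permanently | stop permanently |
| 5.5 to 6.0 | treat, keep dose | treat, keep dose |
| below 5.5 | increase to 25 mg | **no instruction** |

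One branch of three is missing.

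**5. Reach.** The documents give no rate for a first value above 6.0 and not above 6.5. The nearest figure, in the side-effects section, is about 1% with serious hyperkalemia that may lead to discontinuation. On at most 50 patients that is 0.01 × 50 = 0.5 patients. It describes a different group, and the same section expects a considerably higher rate at GFR 40 to 50, so it gives only a rough order of size.

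**The case against.** The strongest reply is that a sensible clinician would not go wrong.

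- **Drug.** Section 10 describes factors that "can contribute to hyperkalemia in addition to the study medication". That fits spironolactone and not a potassium binder. Sections 9.1 and 9.3.3 raise patiromer to control potassium, and the only dose-specific branch in Section 10.3 names spironolactone. This stands as evidence of intent. A reader might infer that the protocol means to withdraw patiromer after hyperkalemia; the documents do not support that. What remains is that the operative sentences do not say so, and Section 9.1 defines the term the other way.
- **Threshold.** The recheck line is complete in itself, and only one value is in dispute. Both are true, but the hold line still orders the opposite at that value. A reader might also infer that below 5.5 is the correct cut-point because the two-week list seems to side with the hold line. It does not: at 5.5 that list keeps the patient on treatment, and Sections 9.3.3 and 10.2 place 5.5 on the permissive side.
- **6.25 mg.** It is tempting to say that such a patient has no onward instruction at all. That goes too far, since two branches apply at any dose. In the third, staying on 6.25 mg is the natural reading, and Section 9.3.3 gives the physician discretion. This part is a minor omission.
- **Relevance.** Enrollment has been closed permanently (COVID-19 management plan, Section 11.3), so few people can be affected. That limits the size of the point but does not remove the fault.

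**Conclusion.** The point holds in a limited form. Section 10.3 contradicts itself at exactly 5.5 mEq/L, and its hold, restart and 50% lines, read with Section 9.1, would withhold and then halve the potassium binder. Those two are faults in a stated safety rule. The missing step at 6.25 mg with potassium below 5.5 is a small gap beside them.

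The size is small. Only participants still in the treatment phase with a first potassium above 6.0 and not above 6.5 come under the restart rule, and the threshold conflict needs a recheck at exactly 5.5. How many that is cannot be derived from the documents. No estimate, test or sample size depends on it. The return from 12.5 to 25 mg when potassium is below 5.5 is a treatment choice and is not in question here. The conclusion rests on the wording alone; it does not assume that patiromer was ever withheld in practice.

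**What to change.** Amend a few lines of Section 10.3:

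1. Use one threshold in both the hold and the restart lines. Below 5.5 is the more cautious choice; at or below 5.5 would match Sections 9.3.3 and 10.2. Either removes the conflict, and the sponsor should choose.
2. Replace study medication(s) with spironolactone in the hold, restart and 50% lines, and state that patiromer is continued and adjusted up to 16.8 g/d under Sections 9.1 and 9.3.3.
3. Add to the two-week list that a patient on 6.25 mg with potassium below 5.5 stays on that dose.

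The cost is a short amendment and a notice to staff. It needs no extra tests, visits or patients, and would apply only to participants still on treatment.
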